# 4 Research Design

This is an open-label maximum tolerated dose (MTD) 3+3 design. 101,102

# Protocol Overview.

Patients will respond to surveys prior to and following cesarean delivery regarding their current pain and mood. Patients will begin study procedures in the third trimester of pregnancy, within approximately one week of scheduled cesarean delivery, until 12-weeks postpartum.

Preoperative weight and vital signs will be measured, and baseline inventories completed (Figure 1; refer to section 1.1). After delivery, cord clamping and declaration of clinical stability by the anesthesiologist (typically~5-15 min after delivery; ±30 minutes), a loading infusion of ketamine 0.05 mg/kg/hour will begin for the first 3-patients in the study. Vital signs and side effect symptomology will be measured 15, 30, and 60 minutes (±5 minutes) after infusion start, and at 4, 8, 10, 12, 16, and 24 hours (±30 minutes) after infusion start. Plasma samples will be collected at 1, 6, 10, and 12 hours (±30 minutes) after infusion. Any report of adverse events or side effects will trigger a blood draw for analysis and correlation of these symptoms to plasma levels of ketamine within the 12-hour infusion. All assessments have been timed to coincide with timing intervals of typical post-CD clinical care interventions. Patients dosing after the first three patients will proceed based on the MTD protocol in Figure 2; refer to section 1.1.

MTD dosing protocol.

A loading dose and maintenance infusion strategy will be used (Figure 2; in section 1.1). MTD to be tested will focus on the initial loading dose used to achieve a higher plasma concentration in a brief period. Ketamine dose will not exceed sub-anesthetic ranges (≤0.2mg/kg/hr). The maintenance rate of 0.05mg/kg/hr is based on our preliminary data suggesting tolerability, and on data suggesting that this rate might yield adequate plasma concentrations necessary for the treatment of depression. The first set of 3 patients will receive a loading infusion of ketamine 0.05 mg/kg/hr for the first data. The decision to escalate the loading infusion dose, enter 3 more at the same level, or stop, will not occur until 3 patients complete the 0.05 mg/kg/hr protocol. A **DLT** event is defined in section 3.4.1.

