# 3.4 Endpoints

# 3.4.1 Primary Endpoint

Maximum Tolerated Dose (MTD). The MTD will be defined as the dose at which fewer than 33% of patients experience a DLT defined by intolerability.

Tolerability (dichotomous Yes/No)

Tolerability (YES) will be defined as: lack of adverse events (adverse event defined as: severe unresolved hemodynamic effect: systolic blood pressure <80 or >160, heart rate <40 or >120).

Lack of Tolerability will be defined as presence of any adverse event (i.e., severe unresolved hemodynamic effect: systolic blood pressure <80 or >160, heart rate <40 or >120).

A **DLT** event is defined by complete infusion cessation due to intolerable side effect acceptability ratings by patient, OR the experience of an intolerable event as defined above. The escalation of dosing will be as noted in Figure 2 and is based on a modified Fibonacci sequence  $^{101,102}$  with smaller proportional increases in dose in the escalation scheme. Escalations occur until 2 in a cohort of 3 to 6 experiences DLT (i.e., until  $\geq$ 33% of patients experience DLT at that dose). The dose **below** this level estimates the MTD.

Participants will be classified as having had a DLT if any of the following conditions are met:

- Persisting (i.e., unresolved after 3 consecutive measurements within a 15-minute interval)
  hemodynamic side effects defined as below and despite treatments or minimizing
  infusion rates as specified.
  - Systolic blood pressure <80 or >160
  - Heart rate <40 or >120
- Complete infusion cessation due to intolerable side effect acceptability ratings by patient

Primary Outcomes will be measured at a minimum of every 4-hours from the start of the ketamine infusion (t = 0) for 24-hours (12-hours post infusion cessation). Additional assessments will be administered between the 4-hour measurements if any adverse event or side effect is noted by the patient.

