# 6.2 Study Drug Preparation and Dispensing

The study drug, ketamine, will be sourced by investigational (IDS) Pharmacy at UPMC Magee Women's Hospital. The infusions will be packaged and labeled for use in the clinical research study per pharmacy protocols and guidelines. Ketamine will be prepared by pharmacy with dosing instructions. There will be no blinding.

For on-site preparation and dispensing of the study drugs, the following procedures will be followed. The pharmacist of record will: maintain adequate records confirming receipt, expiration dates, or other disposition information on the investigational drug; they will record the name of the individual to whom the drug is shipped, date, quantity, and batch number. They will secure the drug in a locked storage area and monitor to ensure proper storage conditions; they will also complete regular inventory to assure accurate indication of stock on hand, as well as proper recording of stock received, dispensed, and returned. For the patients enrolled for open label pharmacokinetic studies, the pharmacist will generate a label prior to dispensing the study drug, including the date dispensed, quantity and expiration information, drug strength and dose; they will affix the label to the dispensed drug. For dispensing and drug disposition recording, they will record the date dispensed, patient initials or other identifiers, drug treatments, quantity dispensed, initials of dispenser, date and amount of patient returns documented in study records (i.e., returned drug that cannot be re-dispensed). Filing and all drug documentation will occur within study records, medical records, and logs.

Following the cesarean delivery, the initial drug administration (via IV infusion) will begin 15 minutes (± 30 minutes) after cord clamping and declaration of clinical/ hemodynamic stability by the case anesthesiologist after delivery. The maintenance dose will start 60 min (range: +15min) after the initial loading dose. The infusion will be completely stopped 12 hours after the start of infusion. The same infusion pump will follow the patient throughout the postoperative period for 12 hours until completion of the study drug. No manipulation of the infusion pump will occur by the patient. Adjustments to the rate will be at the discretion of the study team and can be physically made by study personnel qualified and trained in these procedures, or by clinical care providers under direct orders from the study team.

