# Ketamine Infusion, Side Effect Measures, and Plasma Sampling Procedures.

Preoperative weight and vital signs will be measured, and baseline inventories completed (Figure 1). After delivery, cord clamping and declaration of clinical stability by the anesthesiologist (approximately 5-15 minutes after delivery, ± 30 minutes), a loading infusion of ketamine 0.05 mg/kg/hr will begin for the first 3-patients in the study. Vital signs and Richmond Agitation Scale (RASS), and self-reports of side effects will be measured 15, 30, and 60 minutes (±10 minutes) after infusion start, and at 4-8-10-12-16-24- hours (±30 minutes) after infusion start. Plasma samples will be collected at 1-6-, 10- and 12- hours (±30 minutes) after infusion start via an indwelling IV catheter to facilitate ease of access. Plasma samples at 1-6-, 10- and 12- hours after infusion start will be used to calculate Cmax, AUC, and Css and to correlate DLTs with these PK parameters. Any report of adverse events or side effects will trigger a blood draw for analysis and correlation of these symptoms to plasma levels of ketamine. All assessments have been timed to coincide with timing intervals of typical post-CD clinical care interventions. Patient dosing after the first three patients will proceed based on the MTD protocol in Section 1.1.

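### Two narrative schedules omit the hour-20 vital signs that the 4-hourly minimum for the primary outcome calls for, and no scheduled check need fall at or soon after the end of the load

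*Combined protocol and SAP*

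**What the plan says.** **The minimum.** Section 3.4.1 states: "Primary Outcomes will be measured at a minimum of every 4-hours from the start of the ketamine infusion (t = 0) for 24-hours". Between those times it adds assessments "if any adverse event or side effect is noted by the patient". Persisting blood pressure or heart rate excursions are one of the two routes to a DLT. The other is complete cessation of the infusion because of unacceptable side effects.

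**The two narrative schedules.** Section 4 (Protocol Overview) states: "Vital signs and side effect symptomology will be measured 15, 30, and 60 minutes (±5 minutes) after infusion start", and then "at 4, 8, 10, 12, 16, and 24 hours (±30 minutes) after infusion start". The Section 7 paragraph on ketamine infusion, side effect measures and plasma sampling gives the early times as "15, 30, and 60 minutes (±10 minutes) after infusion start" and the later ones as "at 4-8-10-12-16-24- hours (±30 minutes) after infusion start". Neither contains hour 20.

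**Other text on the same period.** Appendix 2 marks vital signs, RASS, LSD short form and side effect diary at hours 16, 20 and 24. Appendix 4 lists a payment for vital signs and diary at hour 20. The Section 7 paragraph on acceptability ratings runs the diary 4-hourly to 24 hours. Section 7.5 sets 4-hourly side-effect monitoring for 12 hours after the infusion stops; it says vital signs are monitored over the same period but gives no interval.

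**The load.** Sections 1 and 3.2 make the one-hour load the MTD variable, because the sponsor's data suggest that side effects arise with it. Section 6.2 states: "The maintenance dose will start 60 min (range: +15min) after the initial loading dose".

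**The concern.** The trial has one primary output, the MTD, and it depends on a yes-or-no DLT call in three to six patients per level. An undetected DLT can only make a level look safer than it is.

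Two features of the schedule bear on this. First, the paragraphs that describe the infusion-day procedures contradict Section 3.4.1 and Appendix 2 on how often vital signs are taken after hour 16. Staff who follow Section 4 or the Section 7 infusion paragraph would skip a primary-outcome reading that other parts of the protocol call for. Hour-20 vital signs could then be present for some patients and absent for others.

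Second, the load is what is being escalated, yet no scheduled vital signs are tied to its end. The last early check can come before the load finishes, and the next scheduled one is at 4 hours. A patient need not feel a blood pressure or heart rate excursion, so the patient-noted trigger in Section 3.4.1 does not by itself close that interval.

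**Working it through.** **Inputs.** Required interval: 4 h, from 0 to 24 h (Section 3.4.1). Windows: ±5 min (Section 4) or ±10 min (Section 7 infusion paragraph) for the checks up to 60 min, and ±30 min afterwards. Start of maintenance: 60 to 75 min (Section 6.2). I read that as time from the start of the load, with the loading rate running until maintenance begins.

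**1. Reproduce the stated 4 h.** Appendix 2 vital signs fall at 0.25, 0.5, 1, 4, 6, 8, 10, 12, 16, 20 and 24 h. The largest difference is 20 − 16 = 4 h (also 16 − 12 and 24 − 20), so Appendix 2 meets the minimum nominally. If the ±30 min windows are applied to it, the largest possible gap is 20.5 − 15.5 = 5 h.

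**2. The two narrative schedules.** Both list 0.25, 0.5, 1, 4, 8, 10, 12, 16 and 24 h. The largest difference is 24 − 16 = 8 h, twice the minimum. With windows it is 24.5 − 15.5 = 9 h. On a 4-hourly grid (4, 8, 12, 16, 20, 24) the only missing point is 20. Adding it returns the nominal maximum to 4 h.

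**3. The 60-minute check against the end of the load.** The earliest permitted check is 60 − 5 = 55 min (Section 4) or 60 − 10 = 50 min (Section 7). The latest end of load is 75 min. The check can therefore precede the end of the load by 75 − 55 = 20 min or 75 − 50 = 25 min.

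**4. The interval after that check.**

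| Interval | Calculation | Result |
|---|---|---|
| Nominal, 1 h to 4 h | 4 − 1 | 3 h |
| Widest, ±5 min early window | 270 − 55 = 215 min | 3.58 h |
| Widest, ±10 min early window | 270 − 50 = 220 min | 3.67 h |
| End of load at 75 min to latest 4 h check | 270 − 75 = 195 min | 3.25 h |
| End of load at 60 min to latest 4 h check | 270 − 60 = 210 min | 3.5 h |

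Every entry is below 4 h, so this interval does not breach Section 3.4.1.

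**5. Direction of any effect, by illustration only.** In a standard 3+3, a level passes with 0 of 3 DLTs, or with 1 of 3 followed by 0 of 3. With observed DLT probability p, P(pass) = (1 − p)³ + 3p(1 − p)² × (1 − p)³. Assume a true rate of 30%:

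| Assumed share of DLTs missed | Observed p | P(pass) |
|---|---|---|
| None | 0.30 | 0.343 + 0.441 × 0.343 = 49% |
| 10% | 0.27 | 56% |
| One third | 0.20 | 0.512 + 0.384 × 0.512 = 71% |
| One half | 0.15 | 81% |

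The 30% and the missed shares are assumptions. The documents give no basis for any of them, so the table shows direction and sensitivity and does not estimate the bias.

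**The case against.** The strongest reply is that the protocol does not rely on the scheduled grid alone.

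- The DLT definition in Section 3.4.1 is not limited to scheduled research readings. It needs three consecutive measurements within 15 minutes, which single time points cannot supply, so it already depends on off-schedule readings.
- Table 1 starts rechecks on a blood pressure or heart rate excursion without saying who must find it, and an unresolved one counts as a DLT.
- Section 7.4 discontinues the infusion for readings that stay above the limits despite intervention, and says monitoring follows clinical ketamine standards. Section 9.1 says patients stay monitored for the full 12-hour infusion.
- The Appendix 2 footnote has any adverse event trigger vital signs at any point from 0 to 24 hours, with no condition that the patient notices it.
- Hour 20 is present in Appendix 2, and for side effects in two places in Section 7.

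All of this stands, and it rules out several stronger readings. A reader might infer that hours 16 to 24, or the hours after the load, go unobserved. They do not; the narrower point is that the two paragraphs schedule no vital signs there. A reader might infer that the interval after the load breaches the 4-hourly minimum, but at no more than 3.67 h it does not. A reader might infer that clinical readings cannot count toward a DLT, but nothing excludes them. A reader might also assume that exposure peaks as the load ends. For the first cohort, the loading and maintenance rates in Section 4 are both 0.05 mg/kg/hr, so nothing steps down; the higher levels are in Figure 2, which is not shown. The case for a check at that time rests on the plan's own statement that side effects arise with the load.

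The reply does not remove the conflict over hour 20 or over the early window. Nor does it supply an interval for clinical vital signs, or say that charted readings are collected for the DLT call. A triggered assessment also needs something to trigger it, and for a silent excursion that is a reading.

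**Conclusion.** The point holds in two parts of different weight.

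The first is an internal contradiction in the primary-endpoint schedule. Section 4 and the Section 7 infusion paragraph leave 8 h (up to 9 h with windows) between scheduled vital signs, against the 4 h in Section 3.4.1 and the hour-20 entries in Appendix 2. The early windows also disagree, ±5 against ±10 min. This rests on the text alone. Figure 1 is not shown and could not be compared.

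The second is a design weakness and not a breach. The 60-minute check may come up to 25 min before the load ends, and the next scheduled assessment is at 4 h. This assumes that the load runs until maintenance starts and that Section 6.2 allows that start as late as 75 min.

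Missed DLTs could only push the MTD upward. A reader might take the pass probabilities above as the size of that bias, but the documents do not support this: the share of DLTs missed is unknown, routine monitoring and event-triggered checks may catch most or all of them, and DLTs by infusion cessation would register anyway. The changes are worth making because they cost little and protect the one result the trial is built to give.

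**What to change.** 1. Add hour 20 to the vital-sign times in Section 4 and in the Section 7 infusion paragraph, so that both agree with Section 3.4.1 and Appendix 2. Give the post-infusion vital signs in Section 7.5 the same times, and check Figure 1 against them.
2. Use one early window in Sections 4 and 7. Say also whether the 4-hourly minimum is nominal, since ±30 min windows allow 5 h between adjacent points.
3. Time the 60-minute research assessment to the actual end of the load, and record both clock times.
4. State in Section 3.4.1 that all blood pressure and heart rate values charted from 0 to 24 h, including routine clinical readings, are abstracted and applied to the existing DLT definition.

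None of this changes a dose, a DLT threshold or a treatment rule. The cost is a wording amendment and slightly more data entry, mostly from vital signs already charted, for at most 12 patients.

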# 5 Human Subjects

# 5.1 Subject Population

The maximum tolerated dose (MTD) 3+3 design encompasses blocks of 3 patients allocated to dosing schematics. In this study, we have 4 dosing schematics to be tested. Therefore, a minimum number of 6 and maximum number of 12 patients will participate in this trial.

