# 11 Withdrawal of Subjects and Stopping Rules

This section outlines the criteria that specify when dosing an individual subject, cohort, or trial will be suspended.

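### At 0.05 mg/kg/hr, Section 4 defers the decision to stop until 3 patients complete, although two DLTs in the first 2 already settle the level under 3.4.1

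*Combined protocol and SAP*

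**What the plan says.** The MTD dosing part of Section 4 states: "The decision to escalate the loading infusion dose, enter 3 more at the same level, or stop, will not occur until 3 patients complete". The sentence goes on to name the level it governs: the decision "will not occur until 3 patients complete the 0.05 mg/kg/hr protocol". For patients after the first three, Section 4 refers to Figure 2, which is not reproduced in the text available.

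Section 3.4.1 gives the rule that ends escalation: "Escalations occur until 2 in a cohort of 3 to 6 experiences DLT", which it equates with at least "33% of patients experience DLT at that dose". The dose below the failing one is the MTD estimate. Section 5.1 describes enrolment in "blocks of 3 patients allocated to dosing schematics".

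Section 11 opens: "This section outlines the criteria that specify when dosing an individual subject, cohort, or trial will be suspended". Sections 11.1 and 11.2 then define serious adverse events and set out withdrawal of individual patients. Section 11.3 lists circumstances that may justify suspending or ending the trial. None of these refers to a number of DLTs.

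**The concern.** Section 4 does more than stay silent on early closure. It names stopping as one of three decisions that must wait for 3 patients. If the first 2 patients at 0.05 mg/kg/hr both have a DLT, the DLT count in 3.4.1 has been reached, yet the text still calls for a third infusion before anyone may stop.

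At stake is one postpartum patient's exposure to a level that the trial's own rule will reject whatever happens to her, with no gain for the primary endpoint. Two gaps make this harder to resolve on the day:

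- The word used for finishing the protocol is not defined. It could mean the 12-hour infusion, the 24-hour primary-outcome window or the 12-week follow-up.
- The sentence governs the lowest level. If that level fails, there is no level below to name as the MTD, and Section 6.3 offers only dose adjustments for individual patients.

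**Working it through.** **Inputs**

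- DLT count that ends escalation: 2, in a cohort of 3 to 6 (3.4.1).
- The same rule as a rate: at least 33% (3.4.1).
- Level governed by the waiting sentence: 0.05 mg/kg/hr (Section 4).
- DLT probability p: not given. Assumed values are 12.5%, 20%, 33% and 50%. The lowest borrows the 1/8 in Section 6.3, which is the share of individuals given a lower infusion rate because of side effects. It is not a DLT rate, and the protocol says those data do not represent this population.
- Dosing order: assumed sequential, so that the second DLT is known before the third infusion starts. The documents do not state this.

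**Step 1: reproduce the plan's rule.** 2/3 = 66.7%, 2/4 = 50%, 2/5 = 40% and 2/6 = 33.3%. All are at least 33%, so the count and the rate agree at every cohort size named.

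**Step 2: can the third patient matter?** After 2 DLTs in 2 patients, the third gives either 2/3 or 3/3. Both meet the rule, so her result cannot change the outcome. If the second DLT falls on patient 3, no one is dosed in excess.

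**Step 3: probability at the first level.** The excess is exactly one patient, with probability p × p:

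- 0.125² = 0.0156 (1.6%)
- 0.20² = 0.04 (4%)
- 0.33² = 0.1089 (11%)
- 0.50² = 0.25 (25%)

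**Step 4: conditional extension.** Suppose an expansion block entered after 1 DLT in 3 must also be filled. A DLT in the fourth or fifth patient then leaves 2 or 1 further patients with nothing to decide. The added probability is 3p(1−p)² × [1 − (1−p)²]:

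| p | First three: p² | Expansion term | Sum |
|---|---|---|---|
| 20% | 0.040 | 0.384 × 0.360 = 0.138 | 0.178 |
| 33% | 0.109 | 0.444 × 0.551 = 0.245 | 0.354 |
| 50% | 0.250 | 0.375 × 0.750 = 0.281 | 0.531 |

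The waiting sentence does not require the expansion block to be filled, so only the p² column follows from the text.

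**The case against.** The best defence is that a 3+3 design decides by block. Section 5.1 enrols in threes, 3.4.1 words its count for cohorts of 3 to 6, and 2 of 2 settles the level only by inference. Waiting for 3 patients also guards against premature escalation, and a full block describes the failed level's DLT rate better. The plan has other safeguards. Section 13.3 has the investigator review safety data continuously, Sections 7.4 and 10.1 let the DSMB set how often DLT data are monitored, and 11.3 lists unacceptable risk, and the primary endpoint having been reached, among possible grounds for suspension.

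Much of this stands, and it limits the size of the point. It does not remove it. Protection against early escalation needs a wait for escalation and expansion, not for stopping. The routes in 11.3 are permissive and carry no DLT count, whereas Section 4 gives a direct instruction to wait.

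Three stronger readings are tempting, and the documents do not support them:

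- A reader might infer that every level and every expansion must be filled after a second DLT, giving the 18%, 35% and 53% above. The sentence names 0.05 mg/kg/hr only, and the rest depends on Figure 2, which is not shown.
- A reader might infer that a patient whose infusion is stopped for a DLT never counts toward the 3. That is strained: Section 1 counts patients by complete primary outcome data, which a DLT patient has, and 3.4.1 counts DLTs within the cohort. The word still needs a definition, because Section 11 replaces withdrawn patients 1:1 without saying that a DLT patient is not among them.
- A reader might say that the MTD is the level below in either case. At the lowest level there is none.

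**Conclusion.** The point holds at the first level. As written, Section 4 delays the decision to stop at 0.05 mg/kg/hr until 3 patients have completed, and after DLTs in the first 2 the third patient cannot affect the result. The size is one patient, with probability between 1.6% and 25% for assumed DLT rates of 12.5% to 50%, given sequential dosing. The larger figures are correct arithmetic but apply only if expansion blocks must also be filled. Section 11 does not supply the cohort criterion that it announces. This is a modest and inexpensive correction. It does not change how the MTD is derived.

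**What to change.** Reconcile Sections 4 and 11 with the two-DLT count already in 3.4.1:

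1. In Section 4, let the wait for 3 patients apply to escalation and expansion only, and say that enrolment at a level closes once its second DLT is recorded.
2. Replace the undefined notion of completing with evaluable for DLT: the 24-hour primary-outcome window finished, or a DLT at any time.
3. Enter the same closure rule in Section 11 as the cohort criterion promised there.
4. Confirm that Figure 2 applies the rule to later levels and expansions.
5. State the trial-level consequence if 0.05 mg/kg/hr fails. Which consequence is right is for the sponsor to decide.

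The cost is a few sentences. A failed level may hold fewer patients, so its DLT rate is less precisely described. The stated minimum of 6 patients in Section 5.1 should be checked at the same time: a first level that fails in its first block already ends escalation at 3 patients, and with closure at the second DLT it could end at 2.
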